9.6 Endpoint Assessments

9.6.1 General Considerations

The primary analysis of the primary endpoint will be based on the FAS population, while the analysis of the primary endpoint based on the PP population will be considered supportive and serve as one of the sensitivity analyses.

The analysis of all the secondary and exploratory endpoints except the safety endpoints (i.e. adverse events, clinical chemistry and haematology parameters) will be performed for the FAS population. The safety endpoints will be analysed for the safety analysis set unless otherwise noted.

Statistical tests will be performed using a two-sided test at a 5% significance level. Treatment differences will, where appropriate, be presented with 95% confidence intervals and p-values corresponding to the statistical test of the hypothesis of “equal effect” against the alternative of “different effect”.

Continuous variables will be presented with number of subjects, mean, standard deviation, median, inter-quartile range, minimum, and maximum. Categorical variables will be presented with number and percentage of subjects within each specific category.

Missing Data

Missing data from the MRI

If a subject is prematurely discontinued during or after cycle 2, an end-of-treatment MRI examination will be performed. The results from this end-of-treatment MRI will be used.

If the end-of-treatment MRI examination is not performed or is missing, the missing measurement will be imputed using a multiple imputation strategy. The imputation will be based on a missing-at-random assumption using baseline MRI results and some other measurements. The precise imputation strategy will be described in the SAP.

Missing data for adverse events

For adverse events, missing values will be treated as missing, except for causality, intensity, seriousness and outcome of adverse events, where a worst-case approach will be used.

9.6.2 Primary Endpoint

For each type of lesion (endometrioma, DIE and adenomyosis), the primary endpoint is the change in the sum of the lesion sizes at cycle 4, i.e. the difference between the active treatment group and the placebo group in the change from baseline in the sum of the lesion sizes of the same type at the end of cycle 4. The baseline is defined as the sum of the sizes of all lesions of the same type ≥ 10 mm obtained from the MRI examination at screening. At end-of-treatment / cycle 4, the sizes of all lesions included at baseline of the same type will be summed. For each type of lesions, subjects with at least one lesion of that type ≥ 10 mm at baseline will be included.

For each type of lesions, the primary endpoint will be analysed using an analysis of covariance (ANCOVA) model, with the change in the sum of lesion sizes from baseline measured at cycle 4 as the dependent variable, the baseline sum of lesions as covariate, the treatment group and site as fixed effect. The treatment difference between active treatment versus placebo will be reported with 95% confidence interval and corresponding p-value for each of the three types of lesions:

$$\begin{cases} H_0^{P1} : \mu_{QVR}^1 = \mu_{Placebo}^1 \\ H_1^{P1} : \mu_{QVR}^1 \neq \mu_{Placebo}^1 \end{cases}$$

$$\begin{cases} H_0^{P2} : \mu_{QVR}^2 = \mu_{Placebo}^2 \\ H_1^{P2} : \mu_{QVR}^2 \neq \mu_{Placebo}^2 \end{cases}$$

$$\begin{cases} H_0^{P3} : \mu_{QVR}^3 = \mu_{Placebo}^3 \\ H_1^{P3} : \mu_{QVR}^3 \neq \mu_{Placebo}^3 \end{cases}$$

Where (H_0^{P1}) , (H_0^{P2}) , (H_0^{P3}) are the null hypotheses for each of the 3 types of lesions, (H_1^{P1}) , (H_1^{P2}) , (H_1^{P3}) are the alternative hypotheses for each of the 3 types of lesions, and

$$\begin{cases} \mu_{QVR}^1 = \text{The mean change from baseline in the sum of the size of the endometrioma lesions at cycle 4 for QVR} \\ \mu_{QVR}^2 = \text{The mean change from baseline in the sum of the size of the DIE lesions at cycle 4 for QVR} \\ \mu_{QVR}^3 = \text{The mean change from baseline in the sum of the size of the adenomyosis lesions at cycle 4 for QVR} \\ \mu_{placebo}^1 = \text{The mean change from baseline in the sum of the size of the endometrioma lesions at cycle 4 for placebo ring} \\ \mu_{placebo}^2 = \text{The mean change from baseline in the sum of the size of the DIE lesions at cycle 4 for placebo ring} \\ \mu_{placebo}^3 = \text{The mean change from baseline in the sum of the size of the adenomyosis lesions at cycle 4 for placebo ring} \end{cases}$$

In order to control the overall type I error at 5%, the Hochberg procedure is implemented by ranking the 3 p-values in a decreasing order. If the largest p-value is ≤ 0.05 , superiority is established for all 3 types of lesions. If the largest p-value is > 0.05 , but the middle p-value is ≤ 0.025 , superiority is established for the two types of lesions with the smaller p-values. If the largest p-value is > 0.05 and the middle p-value is > 0.025 , but the smallest p-value is ≤ 0.0125 , superiority is established for only the type of the lesion with the smallest p-value. If the largest p-value is > 0.05 , the middle p-value is > 0.025 , and the smallest p-value is > 0.0125 , superiority is not established for any of the 3 types of lesions.

The primary analysis is based on the FAS including those missing the end-of-treatment MRI results. As described above, missing values will be imputed using a multiple imputation strategy.

Sensitivity Analyses

The following sensitivity analyses will be conducted:

1. To test efficacy in more perfect conditions:
 - The primary analysis in the PP population
2. To test sensitivity to missing data:
 - The primary analysis performed on completers (defined as subjects who have completed the scheduled treatment and have both a baseline and a cycle 4 MRI)
 - The primary analysis performed on subjects with both a baseline and an end-of-treatment MRI
 - The FAS using multiple imputation for missing data in a placebo-based pattern mixture model (based on a missing-not-at-random condition) as described by Ratitch

3. The primary analysis using the actual treatment rather than the planned treatment
4. The primary analysis using also lesions that are <10 mm at baseline
5. The primary analysis adjusted for the type of previous hormonal treatment

9.6.3 Secondary Endpoints

The percentage change in the sum of lesion sizes by type, will be analysed using a similar ANCOVA model as the primary endpoint, but both the baseline and the cycle 4 / end-of-treatment results will be log transformed prior to analysis. The estimated difference between treatment groups will be back transformed to ease interpretation.

Secondary endpoints related to proportion of lesions and proportion of subjects with a decrease in a size of ≥ 5 mm at cycle 4 will be based on all lesions ≥ 10 mm at baseline and will be analysed using logistic regression for binary data with logit link function. The generalised estimating equation (GEE) approach will be used to account for correlated data where appropriate.

Count data related to the number of new / disappearing lesions by type, based on all lesions, will be analysed with repeated measures negative-binomial regression using a GEE approach. The regression analysis will be performed with log link function using the appropriate off-set.

Changes from baseline in the volume of endometrioma/DIE lesions assessed by MRI at cycle 4 and in the sizes of endometrioma assessed by TVU at cycle 4 will be analysed similarly to the primary endpoint, but sensitivity analyses will not be performed for these secondary endpoints.

Secondary endpoints related to PROs (B&B, NRS and EHP-30) and endocrine parameters will be analysed using a repeated measures ANCOVA model, with the change from baseline at each post-baseline time point as the dependent variable, the baseline value as a covariate, and the treatment group and treatment by time as fixed effect. The error-covariance matrix will be unstructured.

Changes in the menstrual bleeding pattern will be analysed by investigating the time to first event of change in bleeding pattern using the proportional odds regression model.

Plasma concentration of quinagolide and its metabolites will be analysed descriptively. A population pharmacokinetic modelling method will be outlined in a modelling analysis plan under the responsibility of the Translational Medicine Department of Ferring Pharmaceuticals A/S and the results will be reported separately.

All analyses and respective definitions of the endpoints will be further detailed in the SAP.

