In this trial, there are three sub-groups of subjects, with each sub-group representing one sub-type of lesions, i.e. endometrioma, DIE and adenomyosis. Epidemiology studies have shown that endometriosis and adenomyosis can often coexist in the same subject.^{37,38} Since MRI can assess all pelvic compartments comprehensively at one time, it is feasible and convenient to examine any of the three sub-types of lesions presented in the subject in one MRI examination. The design of three separate sub-groups, with subjects on placebo in each sub-group, can ensure changes in each sub-

type of lesions are assessed against placebo and thereby help identify the sub-type of lesions that responds best to the treatment.

Although a multi-centre setting can help guarantee that the required number of subjects can be recruited within a reasonable time and also support the subsequent generalisation of the results, this trial is limited to a few trial centres with machines of high field strength (3T) and of limited brands to minimise variability of results. In addition, the standardisation of the MRI preparations, sequences and procedures in the trial-specific MRI manual, cross calibration among sites as well as the central reading and analyses of images by the same specialised laboratory have to a great extent been incorporated in the design of this trial to minimise variations across sites.

The treatment period of the trial lasts for four menstrual cycles, which approximately corresponds to the active treatment duration of 18-20 weeks in the second-look laparoscopy study, where significant reductions in endometriotic lesions were observed following oral administration of quinagolide up to 75 µg.

A non-hormonal single-barrier contraception method (i.e. condom) is required for subjects participating in the present trial. Condom is the only feasible contraception method in this trial, as other contraception methods such as oral contraceptives and intrauterine devices (IUDs) can potentially interfere with the assessment of lesions. Throughout the trial, contraception counselling and condoms will be offered to avoid occurrence of pregnancy during treatment. As a precautionary measure, a urine pregnancy test will be performed once per menstrual cycle in the present trial. If the test result is positive and is confirmed by a serum β hCG test, the subject will be discontinued from the trial immediately.

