4.2.2 Randomisation

At the RM+7 visit (visit 2) of cycle -1, eligible subjects will be randomised in a 2:1 ratio to quinagolide vaginal ring dose load 1080 µg or placebo vaginal ring, administered once per menstrual cycle and sequentially for four menstrual cycles (cycles 1, 2, 3 and 4).

An independent statistician will create a computer-generated randomisation list and randomisation is performed centrally through the Interactive Response Technology (IRT) system prior to the insertion of the first vaginal ring. Thereby each subject will receive a unique randomisation number generated in the IRT system. Randomisation is stratified by site.

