4.6 Listing

The subjects screened but not randomized/allocated to treatment will be presented with the reason(s) for screen failure in a data listing.

Based on the combined FAS, subject disposition with respect to analysis sets will be listed by site, treatment and subject number, this listing will include information on in which subgroup the subject was allocated to at randomisation. Subjects who discontinued from the trial will be listed by site, treatment, and subject number including information on timing of and reason for discontinuation.

5 Protocol Deviations

Protocol deviations will be rated as either minor or major. Protocol deviations impacting the primary endpoint and thereby affecting the conclusions of the trial will be rated as major. Major protocol deviations will lead to exclusion of data from the per protocol (PP) analysis sets. Data will not be excluded from the data analysis in case of minor protocol deviations.

The list of major protocol deviations includes, but is not restricted to:

- Treatment received not in accordance with randomisation
- Non-compliance with investigational medicinal product (IMP) treatment regimen for >20% of days during the non-menstrual period. The non-menstrual period of each cycle (cycle 1 to 4) is defined as the period from stop date of menstrual bleeding (excluding the stop day) to start of menstrual bleeding (excluding the start date). For a given cycle the stop date is based on the menstrual bleeding pattern form obtained at the beginning of the cycle, and the start date of menstrual bleeding is based on the menstrual bleeding pattern form obtained at the end of the cycle. The calculation of non-compliance percent is based on the combined non-menstrual period for cycle 1 to 4. In case of missing information on start and/or stop dates, the entire cycle in question will be considered as non-menstrual.

Unforeseen deviations deemed to impact the primary endpoint of the trial may additionally be rated as major protocol deviations by the Ferring clinical team, with support from the Syneos team, on the basis of a blinded review of data before declaration of clean-file and lock of database.

The list of major protocol deviations will be detailed and documented in the clean file document prior to database lock.

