6.1 Full Analysis Sets

For this trial five full analysis sets (FAS) will be defined. One for each of the three types of lesions, one for endometriosis (endometrioma and DIE combined) and one for all three types of lesions combined (referred to as the combined FAS).

For the analysis of endometrioma, the FAS comprises of all randomised and treated subjects with at least one endometrioma lesion ≥ 10 mm at baseline.

For the analysis of DIE, the FAS comprises of all randomised and treated subjects with at least one DIE lesion ≥ 10 mm at baseline.

For the analysis of adenomyosis, the FAS comprises of all randomised and treated subjects with a maximum junctional thickness ≥ 12 mm at baseline or the size of another adenomyosis lesion ≥ 10 mm at baseline.

For the analysis of endometriosis, the FAS comprises of all randomised and treated subjects with at least one endometrioma lesion ≥ 10 mm at baseline and/or at least one DIE lesion ≥ 10 mm at baseline (referred to as the endometriosis FAS).

For the analysis of the three types combined, the FAS comprises of all randomised and treated subjects.

Treatment assignment for summaries and analyses are according to planned treatment. The study was planned to be have a randomisation ratio of 2:1 with 2 subjects receiving quinagolide vaginal ring for each subject receiving placebo vaginal ring, however the randomisation list used during the study had a 1:1 ratio between quinagolide placebo and placebo vaginal ring. The planned treatment used in the FAS is the treatment according to the actually used randomisation list.

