9.3.4 Other Secondary and Exploratory Endpoints

All summaries in this section will be performed by treatment and in total. As indicated in [Table 9-1](#) some endpoints will be summarised and analysed for each of the three types of lesion (endometrioma, DIE and adenomyosis) and for endometriosis (endometrioma and DIE), some for all types of lesion combined, and some for both.

No imputation will be done for the analysis of these other secondary and exploratory endpoints. The endpoint derived from the MRI will, however, use the end-of-treatment assessment even if the end-of-treatment assessment is performed before end of cycle 4.

Table 9-1 Analyses of Other Secondary and Exploratory Endpoints

Endpoint	Analysis method					Presentation	
	ANCOVA	Repeated measures ANCOVA	Logistic regression	Negative Binomial regression	Proportional odds	By type of lesion and disease	All types of lesions combined
Proportion of lesions by type with a decrease in a size of ≥ 5 mm on MR images at cycle 4			X			X	
Proportion of subjects with a lesion of any type decreased in a size of ≥ 5 mm on MR images at cycle 4			X				X
Number of new endometrioma, DIE and adenomyosis lesions by type on MR images at cycle 4				X		X	
Number of disappearing endometrioma, DIE and adenomyosis lesions by type on MR images at cycle 4				X		X	
Changes in the total physical sign pain score and change in the total symptom and sign severity score of the Biberoglu and Behrman (B&B) scale at cycle 4	X					X	X
Changes in the Numerical Rating Scale (NRS) pain scores at cycles 1, 2, 3 and 4		X				X	X
Changes in each of the five EHP-30 scores and the total EHP-30 score per cycle at cycles 2 and 4		X				X	X
Changes in the menstrual bleeding pattern over 4 cycles		X			X	X	X
Change in serum levels of prolactin, TSH, IGF-1 during cycle 1, at cycles 2 and 4		X				X	X
Changes in the sizes of uterine fibroids on MR images at cycle 4	X						
Changes in the sizes of uterine fibroids assessed by TVU at cycle 4	X						
Changes in circulating levels of VEGF, PIGF, IL-6, CA125 and sFlt-1 at cycle 4	X					X	X

Note: Exploratory endpoints are shaded in grey.

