9.3.4.3 Continuous Endpoints

The analysis of the secondary endpoints related to PROs (B&B, NRS, and EHP-30), endocrine parameters (prolactin, TSH, and IGF-1), serum endometriosis biomarkers (VEGF, PIGF, IL-6, CA125, and sFlt-1), sizes of uterine fibroids (the sum of the size of all fibroids) assessed by MRI and TVU, will be described in this subsection.

The absolute value at baseline and the absolute value at each post baseline measurement, and the change from baseline to each post baseline measurement will be summarised. These endpoints will be analysed using a repeated measures ANCOVA model, with the change from baseline at each post-baseline time point as the dependent variable, the baseline value as a covariate, and the treatment group and treatment group by time as fixed effects. The error-covariance matrix will be unstructured. For the endpoints only measured once post baseline, an ordinary ANCOVA similar to the one used in the primary analysis will be applied (without imputations). The analyses will be performed for each of the three types of lesions, and for endometriosis (endometrioma and DIE). The treatment difference between active treatment versus placebo will be reported with 95% confidence interval and corresponding p-value for each post baseline of these endpoints.

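### The all-types-combined models for symptoms, quality of life, hormones and biomarkers have no term for lesion sub-group; adding it is a low-severity, nearly free gain in precision

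*Protocol*

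**What the plan says.** **Model.** Protocol 9.6.3 analyses B&B, NRS, EHP-30 and the endocrine parameters by repeated measures ANCOVA of change from baseline, with "the baseline value as a covariate, and the treatment group and treatment by time as fixed effect". SAP 9.3.4.3 keeps the same terms: "the baseline value as a covariate, and the treatment group and treatment group by time as fixed effects". Endpoints measured once after baseline get an ordinary ANCOVA like the SAP's primary model, which has baseline and treatment only. Protocol 9.6.4 covers the circulating biomarkers.

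**Population.** SAP 9.3.4 says that endpoints will be summarised and analysed by type and disease, "some for all types of lesion combined, and some for both". Table 9-1 marks the B&B, NRS, EHP-30, endocrine and biomarker rows under both headings. SAP 6.1 defines the pooled set: "For the analysis of the three types combined, the FAS comprises of all randomised and treated subjects". However, SAP 9.3.4.3 itself says only "The analyses will be performed for each of the three types of lesions, and for endometriosis (endometrioma and DIE"), with no mention of a pooled analysis.

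**Sub-group.** About 24 women are planned in each of three sub-groups. The allocation is recorded; SAP 4.6 says of the disposition listing that "this listing will include information on in which subgroup the subject was allocated to at randomisation".

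**Randomisation.** Protocol 4.2.2 states "Randomisation is stratified by site" and names no other factor. The Protocol synopsis, Protocol 1.3, Protocol 3.1.2 and SAP 3.1 describe women being randomised within each sub-group.

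**The concern.** The combined analyses are the largest comparisons available for these endpoints. They pool women with DIE, adenomyosis and endometrioma, and the model does not use the factor by which the trial was organised. If mean change differs between sub-groups after the baseline covariate, that difference stays in the residual and the intervals are wider than they need be.

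The consequence depends on how the list was built. If sub-group was a stratum, the model omits a stratification factor. If it was not, a chance imbalance in lesion type can move the treatment estimate in this particular trial.

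The SAP does adjust one pooled analysis for a lesion characteristic: in SAP 9.3.4.1, the proportion of women with a decrease of at least 5 mm is adjusted for the number of measurable lesions at baseline. The pooled continuous models have no counterpart.

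**Working it through.** **1. Are combined models planned?** SAP 9.3.4 uses both verbs, summarised and analysed; Table 9-1 ticks the combined column; SAP 6.1 defines the set. One sentence in SAP 9.3.4.3 leaves the combined analyses out. Read together, combined models are planned and the two SAP places need reconciling.

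**2. The plan's own power figure.** The only stated power is for the primary endpoint: 83% for 16 against 8 women, difference 6 mm, SD 4.5 mm, two-sided 5% t-test (Protocol 9.1). Noncentrality is 6 / (4.5 × √(1/16 + 1/8)) = 3.08 on 22 df, giving 83.7%, so it reproduces. All 14 cells of Protocol Table 9-1 also reproduce. No power is stated for the combined secondary models.

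**3. Gain from adding sub-group.** Assumptions: N = 72, 24 per sub-group, 36 per arm under the 1:1 list. R² is the share of the variance left after the baseline covariate that sub-group explains. The documents give no R², so a range is shown. With three equally spaced sub-group means, R² = 0.02 corresponds to steps of √(0.02 × 3/2) = 0.17 SD, and R² = 0.20 to √(0.20 × 3/2) = 0.55 SD.

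- Planned model: 72 − 3 = 69 df. The effect with 80% power is 0.670 SD.
- Adjusted model: 67 df, residual SD multiplied by √(1 − R²).
- Interval width ratio: √(1 − R²) × t(0.975; 67) / t(0.975; 69).

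| R² | Power, planned | Power, adjusted | Change in interval width |
|---|---|---|---|
| 0 | 80% | 80.0% | +0.1% |
| 0.02 | 80% | 80.8% | −1.0% |
| 0.05 | 80% | 81.9% | −2.5% |
| 0.10 | 80% | 83.9% | −5.1% |
| 0.20 | 80% | 87.9% | −10.5% |

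At 48/24 the effect with 80% power is 0.710 SD, and the table is the same to this rounding.

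**4. Imbalance, only if sub-group was not a stratum.** The number of women from one sub-group in a 36-woman arm is hypergeometric, with SD √(36 × 1/3 × 2/3 × 36/71) = 2.01. The between-arm difference in that sub-group's share has SD 2 × 2.01/36 = 0.112, or 11 percentage points (12 at 48/24). By simulation, at least one of the three shares differs by 15 points or more in 42% of trials at 1:1 (38% at 2:1), and by 20 points or more in 18% (15%). The effect on the estimate is small: a 15-point imbalance with a 0.5 SD difference between types moves it by 0.15 × 0.5 = 0.075 SD.

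**5. Imbalance and added variance are one quantity.** In units of the unadjusted residual SD, the variance of the estimate falls on adjustment by R² × (1/36 + 1/36). The variance of the shift caused by random imbalance is R² × 72/71 × (1/36 + 1/36). At R² = 0.10 these are 0.0056 and 0.0056. The shift has SD 0.075, against an unadjusted standard error of √(2/36) = 0.236, which already includes it.

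**6. Type I error.** In 4,000 simulated 1:1 trials per setting without stratification, the unadjusted test rejected 4.6% of the time at R² = 0.05 and 5.6% at R² = 0.20 (Monte Carlo standard error about 0.35 points).

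**The case against.** Four stronger readings are tempting, and the objection to each stands.

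- **That randomisation left the arms unbalanced on lesion type.** A reader of Protocol 4.2.2 alone might infer this. The synopsis, Protocol 1.3, Protocol 3.1.2 and SAP 3.1 describe randomisation within each sub-group, and Protocol 3.5.1 relies on placebo women in each. The conflict is unresolved, so step 4 is conditional.
- **That the design expects type to affect these outcomes.** Protocol 3.5.1 says the three sub-groups "thereby help identify the sub-type of lesions that responds best to the treatment", but this is about lesion change. Protocol 9.1 assumes an equal treatment effect across types. A best-responding type is also a matter of treatment interaction, which a main-effect term does not address. No section links type to change in pain, quality of life or hormones.
- **That the estimate is biased or the test invalid.** Steps 5 and 6 show otherwise.
- **That imbalance and extra variance are two separate harms.** They are the same variance, and the unadjusted interval already allows for it.

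These endpoints are also secondary or exploratory, lie outside the Hochberg family, and are analysed by lesion type as well, so between-type differences will be visible.

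The objection does not remove the point itself. The by-type analyses do not sharpen the combined estimate. The equal-effect assumption does not argue against a main-effect covariate, which needs only different average change by sub-group. The adjustment costs almost nothing if sub-group proves irrelevant.

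**Conclusion.** The omission is real and of low severity; correcting it is a free improvement. Combined models are planned without a recorded three-level design factor. The benefit is precision only and depends on an R² that the documents do not give: power of about 81% to 88% instead of 80% for R² from 0.02 to 0.20, with intervals about 1% to 10% narrower, and intervals about 0.1% wider if R² is zero.

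These figures assume the planned 72 women in equal sub-groups; the SAP does not give the actual total. The documents do not support a claim that the arms are unbalanced on lesion type, or that lesion type is known to influence these endpoints. The reason given in SAP section 12 for dropping site from the primary model, that four of six sites have four or fewer women, would not apply to three sub-groups of about 24.

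**What to change.** Before unblinding:

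1. Add lesion sub-group as recorded at randomisation (DIE, adenomyosis, endometrioma) as a fixed factor in every all-types-combined ANCOVA and repeated measures ANCOVA: Protocol 9.6.3 for the PROs and endocrine parameters, Protocol 9.6.4 for the biomarkers, and SAP 9.3.4.3 for all of them. Yes/no indicators for each lesion type are an alternative. Sub-group labels follow a rarity ranking and can overflow when a group is full (Protocol 7.1.1), and a woman may have more than one type.
2. Name the combined analyses in SAP 9.3.4.3 so that it agrees with SAP Table 9-1.
3. State whether the randomisation list actually used was built by sub-group, by site, or by both, and reconcile Protocol 4.2.2 with the sections that describe randomisation within sub-group.
4. Leave the by-type models unchanged.

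The cost is a line or two of SAP text and 2 of about 69 residual degrees of freedom. No new data are needed.
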